4.2 Scientific Rationale for Study Design

Screening Cycle: Visit 2 to Visit 3

Participants will be dispensed an eDiary and rescue medication at Visit 2 and instructed on their use. The information collected during the SC will allow the investigator to ascertain and verify that the participant meets requirements for study entry (ie, length of menstrual

cycle, average pelvic pain score, compliance with eDiary entries, and compliance with rescue and other pain relief medications) as noted in the Inclusion Criteria (Section 5.1).

Baseline Cycle: Visit 3 to Visit 4/Day 1

At Visit 3, single-blind placebo run-in medication will be dispensed. Thus, in addition to continued monitoring to ensure the participant meets inclusion criteria as noted above, this baseline menstrual cycle has the purpose of familiarizing the participants with the study treatment regimen and excluding participants with a placebo response (ie, participants who have an average pain score during the SC of ≥ 5 , and average pain score during the BC of < 5 , as measured by the NRS in the Daily eDiary). In addition, participants who are not compliant with the blinded placebo before randomization will be excluded. Baseline measurements for change from baseline analyses will be obtained during this cycle.

Treatment Cycle 1 and 2: Visit 4/Day 1 to Visit 6

TRC1 and TRC2 provide 2 complete menstrual cycles to evaluate the safety and efficacy of MK-7264. Two cycles have been proposed as an adequate timeframe for the efficacy of the medication to be observed. The primary efficacy will be assessed by the change from baseline in average daily pelvic pain score (cyclic and non-cyclic) during TRC2. Efficacy will also be assessed at TRC1 via an exploratory objective.

Post-treatment Cycle: Visit 6 to Visit 7

The purpose of the PTC is to assess the pain scores after participants have stopped double-blind study intervention. Pain scores from the PTC will be compared to pain scores from the SC, as the participants will be under the same clinical circumstances (ie, only rescue medication being used as needed) during both cycles.

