Note: Pain severity score will be measured using 0-10 NRS anchored with 0 (no pain) and 10 (extremely severe pain).

12. Participant has demonstrated compliance with $\geq 75\%$ of daily eDiary entries (ie, pelvic pain score, vaginal bleeding, rescue medication intake, intake of pain relief medication other than naproxen sodium provided by Sponsor, and impact of pelvic pain) during the SC.

Note: eDiary compliance will be automatically calculated by the eDiary vendor partner and a report will be provided. The investigational site should review the report before the participant's scheduled visit to assess eligibility.

13. Participant has taken only the study provided rescue medication, at a dose not exceeding the maximum dose determined by the investigator according to the local label, for control of ERP during the SC as evidenced in the eDiary.

Note: Short term use (ie, ≤ 3 days) of other non-opioid pain medications for acute conditions other than ERP is permitted.

At Visit 4 (Before Randomization)

14. Participant's menstrual cycle before Visit 4 (BC) was 24 to 38 days (inclusive) as documented in the eDiary.
15. Participant reports at least moderate pelvic pain during the BC as defined by average daily pelvic pain (cyclic and non-cyclic) score ≥ 5 .

Note: Pain severity score will be measured using 0-10 NRS anchored with 0 (no pain) and 10 (extremely severe pain).

16. Participant has demonstrated compliance with $\geq 75\%$ of daily eDiary entries (ie, pelvic pain score, vaginal bleeding, rescue medication intake, intake of pain relief medication other than naproxen sodium provided by Sponsor, and impact of pelvic pain) during the BC.

Note: eDiary compliance will be automatically calculated by the eDiary vendor partner and a report will be provided. The investigational site should review the report before the participant's scheduled visit to assess eligibility.

17. Participant is $\geq 80\%$ compliant with the placebo run-in medication (as determined by site-performed tablet count).
18. Participant has taken only the study provided rescue medication, at a dose not exceeding the maximum dose determined by the investigator according to the local label, for control of endometriosis-related pelvic pain during the BC as evidenced in the eDiary.

Note: Short term use (ie, ≤ 3 days) of other non-opioid pain medications for acute conditions other than ERP is permitted.

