6.3.2 Stratification

Treatment allocation/randomization will be stratified according to the following factors:

- Severity of pelvic pain
 - Moderate (ie, average score of ≥ 5 to < 8 on the NRS in the eDiary during the BC), or
 - Severe (ie, average score of ≥ 8 on the NRS in the eDiary during the BC)

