8.10.2 Placebo Run-In

Participants will return for Visit 3 on the first non-menstrual day after the SC menses. If the participant meets Visit 3 eligibility criteria, she will enter a single-blind, placebo run-in

period of approximately 4 weeks (ie, the duration of BC). The run-in period will end on the last day of menses of the BC, and the participant will return to the site the next day for Visit 4 (randomization).

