3.6.1 Statistical Methods for Efficacy Analyses

This section describes the statistical methods that address the primary and secondary objectives. The primary analysis will be based on the FAS population, and supportive analyses will be based on the mFAS, Completer population and PP population.

The efficacy analyses will be performed based on the available data during 5 cycles, defined as below:

- Screening Cycle (SC):
 - Starts the first non-bleeding day of the SC (i.e., 1 day after the last day of the menses before Visit 2) and ends the last bleeding day of SC.
- Baseline Cycle (BC) placebo run-in period:
 - Starts on the first non-bleeding day of the BC (i.e., 1 day after the last bleeding day of the SC) and ends the last bleeding day of BC.
- TRC1 after randomization:
 - Starts on Day 1 (i.e., the first study medication intervention) and ends the last bleeding day of TRC1.
- TRC2:
 - Starts on the first non-bleeding day of TRC2 (i.e., 1 day after the last bleeding day of the TRC1) and ends the last bleeding day of TRC2.
- Post-Treatment Cycle (PTC) after the participant has stopped taking study intervention:
 - Starts on the first non-bleeding day of PTC (i.e., 1 day after the last bleeding day of the TRC 2) or the day after the last dose of study medication, whichever is last and ends the last bleeding day of PTC.

Primary Efficacy Analysis

The primary efficacy endpoint is the average daily pelvic pain score during TRC2. The variable of change from baseline in the average daily pelvic pain score will be used in the analysis of the primary endpoint. The primary analysis approach will be conducted utilizing the longitudinal analysis of covariance (ANCOVA) model. In this model, the response vector consists of the change from baseline in the average daily pelvic pain scores during TRC1 and

TRC2. The model will include factors for average pelvic pain scores at baseline cycle, stratum, treatment, cycle, interaction of stratum-by-cycle, and the interaction of treatment-by-cycle as covariates. The model will use all available daily scores for calculating average pain scores during TRC1 and TRC2. The least-squares (LS) mean change from baseline at TRC2 with the associated standard errors (SEs) will be displayed for each treatment group; and the estimated treatment differences (MK-7264 – placebo) along with corresponding 95% CIs will also be presented.

Secondary Efficacy Analyses

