From the longitudinal ANCOVA model, the response vector consists of the change from screening cycle in the average daily pelvic pain scores during BC, TRC1, TRC2, and PTC. The model will include factors for average pelvic pain scores at screening cycle, stratum, treatment, cycle, interaction of stratum-by-cycle, and the interaction of treatment-by-cycle as covariates. The LS mean (SEs, and 95% CIs) will be presented.

- Average daily pelvic pain scores (cyclic and non-cyclic, combined and separately) as compared to baseline during TRC1:

The average daily pelvic pain score during TRC1 will be analyzed from the same model (including response vector and covariates) for the primary endpoint, and the LS mean (SEs, and 95% CIs) will be presented in the same way.

For the proportions in the following exploratory endpoints, they will be analyzed by logistic-regression models comparing MK-7264 with placebo, including average pelvic pain scores at baseline cycle, stratum, treatment, cycle, interaction of stratum-by-cycle, and the interaction of treatment-by-cycle as covariates.

- Proportion of participants with at least 1-point (2, or 3) reduction in average daily pelvic pain score (cyclic and non-cyclic, combined and separately) as compared to baseline during TRC2.
- Proportion of participants with at least 1-point (2, or 3) reduction in average daily pelvic pain score (cyclic and non-cyclic, combined and separately) as compared to baseline during TRC2, and no increase in the average daily use of rescue medication by number of tablets.
- Proportion of participants with at least 1-point (2, or 3) reduction in average daily pelvic pain score (cyclic and non-cyclic, combined and separately) as compared to baseline

during TRC2, no increase in the average daily use of rescue medication by number of tablets, and no use of concomitant pain medication.

- Proportion of participants with at least 1-point (2, or 3) reduction in average daily pelvic pain score (cyclic and non-cyclic, combined and separately) as compared to baseline during TRC2, no increase in the average daily use of rescue medication by number of tablets, and no use of concomitant pain medication for ERP.

The following PRO exploratory endpoints will be analyzed using available data.

- Endometriosis Health Profile (EHP)-5:

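### The exploratory post-treatment model fits the pre-randomisation Baseline Cycle as a response with a free treatment effect, so the PTC contrast is not adjusted for the continuous baseline score, at a modest cost in precision

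*Combined protocol and SAP*

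**What the plan says.** sSAP 3.6.1, under exploratory efficacy analyses, specifies a longitudinal ANCOVA for the PTC endpoint in which "the response vector consists of the change from screening cycle in the average daily pelvic pain scores during BC, TRC1, TRC2, and PTC". On the covariate side, "The model will include factors for average pelvic pain scores at screening cycle", together with "stratum, treatment, cycle, interaction of stratum-by-cycle, and the interaction of treatment-by-cycle as covariates". The output named for this model is LS means with SEs and 95% CIs. The covariance structure is not stated there.

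The timing of BC is clear. Protocol 8.10.2: "The run-in period will end on the last day of menses of the BC", with the randomisation visit on the next day. sSAP 3.6.1 defines TRC1 as follows: "Starts on Day 1 (i.e., the first study medication intervention) and ends the last bleeding day of TRC1".

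BC also enters the model in a second way. Protocol 6.3.2 defines the randomisation stratum by an average score below 8, or of 8 and above, "on the NRS in the eDiary during the BC". Entry is restricted as well. Protocol 5.1 requires that "Participant reports at least moderate pelvic pain during the BC", meaning an average of at least 5, and sets the same threshold for SC.

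The primary model in the same sSAP section treats BC differently: the BC average is a covariate, and only TRC1 and TRC2 are responses.

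**The concern.** All women take single-blind placebo in BC and are randomised after it, so any BC difference between arms is chance. The PTC model nevertheless gives each arm its own BC mean. Nothing in the documents constrains that difference to zero or explains why BC is a response here when it is a covariate in the primary model.

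Fitting BC this way prevents it from doing the work of a baseline. When each response has its own free arm means and nobody is missing, one response tells the model almost nothing about the arm difference in another. The continuous BC average is the most recent pre-randomisation pain measurement and is available for every randomised woman, yet it is left out of the adjustment of the PTC difference. At stake are the width of the interval for that difference and chance BC imbalance within each stratum.

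**Working it through.** **Plan's own figure.** No power or precision is stated for PTC. The primary power does reproduce: with 70 per arm, difference 1 and SD 2, SE = 2 × √(2/70) = 0.338; 1/0.338 = 2.958; 2.958 − 1.960 = 0.998; Φ(0.998) = 84.1%, against the stated 84%. This confirms the inputs used below but does not bear on the PTC model.

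**Step 1: what BC as a response contributes.** If every covariate had a cycle-specific coefficient, the complete-data fit with an unstructured covariance would equal a separate ANCOVA of each cycle, and BC would contribute nothing to PTC. The plan's SC slope is common across cycles, so the identity is near rather than exact. In simulation the planned model's PTC estimate had empirical SD 0.216, against 0.214 for an ANCOVA of PTC on SC and stratum (equal correlation 0.7), and 0.140 against 0.138 (equal correlation 0.9). The BC response adds essentially nothing.

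**Step 2: gain from continuous BC, closed form.** The variance ratio is 1 − r², where r is the partial correlation of PTC and BC given the other covariates. Take first SC alone as the other covariate, with no stratum and no entry rule:
- equal correlation ρ between all cycles: r = ρ/(1 + ρ);
- correlation ρ^lag, with BC three cycles and SC four cycles before PTC: r² = ρ⁶(1 − ρ²)/(1 − ρ⁸).

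**Step 3: with the stratum and entry rules.** Simulation: 600 trials per setting, 140 women, 1:1 within strata, complete data, mean 6.5 and SD 2 before selection, scores limited to 0-10, SC and BC averages at least 5, stratum cut at BC 8, no true effect, unstructured covariance. The planned model was compared with one that has TRC1, TRC2 and PTC as responses and the SC and BC averages as covariates. The correlations are assumptions and apply before selection.

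| Pattern | ρ | Cut, SC only (step 2) | Partial r given SC and stratum | Cut = r² | Simulated variance ratio, BC as covariate / planned |
|---|---|---|---|---|---|
| Decaying with lag | 0.5 | 1% | 0.05 | 0.3% | 1.007 |
| Decaying with lag | 0.7 | 6% | 0.14 | 2.0% | 0.978 |
| Decaying with lag | 0.8 | 11% | 0.21 | 4.4% | 0.983 |
| Decaying with lag | 0.9 | 18% | 0.32 | 10.2% | 0.877 |
| Equal | 0.5 | 11% | 0.16 | 2.6% | 0.964 |
| Equal | 0.7 | 17% | 0.24 | 5.8% | 0.927 |
| Equal | 0.8 | 20% | 0.29 | 8.4% | 0.895 |
| Equal | 0.9 | 22% | 0.36 | 13.0% | 0.798 |

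The simulated ratios carry Monte Carlo noise, so the r² column is the steadier guide. In SE terms, equal 0.7 goes from 0.216 to 0.208 and equal 0.9 from 0.140 to 0.125.

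**Step 4: a second set of correlations.** With SC-BC 0.6, BC-PTC 0.6 and SC-PTC 0.5, the step 2 approach gives r = (0.6 − 0.6 × 0.5)/√((1 − 0.36)(1 − 0.25)) = 0.3/0.693 = 0.433, a cut of 18.8%. An ANCOVA simulation (3,000 trials) with stratum in both models and the entry rules applied gives 5.6%, SE 0.264 to 0.256. Four other settings, with correlations between 0.35 and 0.7, gave 0.2% to 3.5%.

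**Step 5: bias.** Across the eight settings in the table, the planned estimate's mean was at most 0.023 from zero. That was at decaying 0.7, where the Monte Carlo SE is 0.321/√600 = 0.013. This is consistent with no bias.

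**The case against.** The strongest reply is that BC is not ignored. The stratum is BC cut at 8, randomisation is balanced on it, and stratum-by-cycle gives it its own effect at PTC. A reader might infer from the covariate list that the contrast is adjusted for SC alone; that is wrong. The stratum, together with the narrowed score range after entry at 5 or above, is why the gains in step 3 mostly fall well below those in step 2. What remains is the BC information within strata.

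The second reply is that the objective is a comparison with screening. Protocol 4.2: "Pain scores from the PTC will be compared to pain scores from the SC". The PTC objective in protocol section 3 does not use the drug-versus-placebo wording of the adjacent TRC1 objective, and having BC as a response yields a model-based run-in change from SC. This stands in part. The between-arm PTC contrast is implied by treatment-by-cycle and by the sSAP's intention to analyse continuous exploratory endpoints much as the primary one, but it is not spelled out. Either repair keeps change from SC as the response, and the second also keeps the modelled run-in change.

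A reader might also infer that a BC treatment difference will be reported and read as a drug effect. It is estimable, but the sSAP lists only LS means with SEs and CIs for this model, so the documents do not support that claim.

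**Conclusion.** The point holds as a modest loss of efficiency in one exploratory analysis. With complete data, the PTC contrast forgoes adjustment for the continuous BC average and keeps chance BC imbalance within strata. The variance cut available is roughly 0-6% at between-cycle correlations of 0.5 to 0.7 (7% in one simulated ratio). At 0.8 it lies in between, at about 2-10%, and it reaches about 10-20% only near 0.9. These figures rest on assumed correlations, an assumed mean of 6.5, the planning SD of 2, an unstructured covariance and no dropout. The plan expects 15% dropout, which was not simulated.

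It would be tempting to read this as bias, as inflated type I error, or as a loss near 17-20% in general. None of these follows: the planned estimate is unbiased, and losses of that size appear only if the stratum and entry rules are ignored or the correlations are very high. The primary and secondary TRC2 analyses already use the baseline-cycle score as a covariate and are untouched. This is a desirable improvement, not a necessary one.

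**What to change.** In sSAP 3.6.1, for the PTC model, use one of two specifications:
- Keep change from SC as the response at TRC1, TRC2 and PTC, and add the continuous BC average as a covariate beside the SC average, stratum, treatment, cycle and the two interactions.
- Or keep BC in the response vector and constrain its treatment effect to zero.

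The first matches the primary model and avoids regressing BC on a stratum that is itself BC cut in two. Its small cost is that the BC change from SC becomes a descriptive summary; the second option keeps it model-based. It would also help to state whether the between-arm PTC difference is to be reported.

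The cost is one model statement and a sentence of text. No data are lost, since protocol 5.1 requires a BC average and at least 75% diary compliance in BC before randomisation. Protocol section 9 lets changes to exploratory analyses be documented in the sSAP before unblinding, so no protocol amendment is needed.

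### The exploratory post-treatment model uses the pre-randomisation Baseline Cycle as a response instead of a covariate, which gives up a little precision; the stratum weights for its LS means should also be stated

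*Combined protocol and SAP*

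**What the plan says.** The exploratory part of sSAP 3.6.1 sets out a longitudinal ANCOVA for pain in the PTC relative to the SC. In it, "the response vector consists of the change from screening cycle in the average daily pelvic pain scores during BC, TRC1, TRC2, and PTC". On covariates: "The model will include factors for average pelvic pain scores at screening cycle, stratum, treatment, cycle, interaction of stratum-by-cycle, and the interaction of treatment-by-cycle". On output: "The LS mean (SEs, and 95% CIs) will be presented". The bullet names neither a covariance structure nor the weights given to the two strata in the LS means.

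Three other places bear on the role of the BC:

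- Protocol 8.10.2: "The run-in period will end on the last day of menses of the BC". Randomisation follows at Visit 4.
- Protocol 6.3.2 builds the stratum from the BC average; the upper level is "Severe (ie, average score of ≥ 8 on the NRS in the eDiary during the BC").
- Protocol 4.2 says of the BC: "Baseline measurements for change from baseline analyses will be obtained during this cycle".

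In the primary model (protocol 9.6.1 and sSAP 3.6.1) the BC average is a covariate and the responses are TRC1 and TRC2 only.

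**The concern.** A treatment-by-cycle term that covers the BC fits an MK-7264 effect in a cycle when nobody had taken MK-7264. The true effect there is known to be zero, so estimating it yields nothing. The cost is that the BC average, measured before randomisation and likely to predict PTC pain, enters the adjustment only through a two-level cut at 8. That cut is also a function of one of the responses.

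The stake is precision in the only model specified for the PTC objective. A separate matter concerns the displayed arm-level means. Without the BC average as a covariate, the stratum coefficient at PTC can be large, so the choice of stratum weights can visibly move the LS means.

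**Working it through.** **1. The plan's own figure.** The documents give no power or SD for the PTC analysis. The primary figure (sSAP 3.9) reproduces: 70 per arm, difference 1, SD 2, two-sided 0.05 gives Φ(1/(2√(2/70)) − 1.960) = Φ(2.958 − 1.960) = Φ(0.998) = 0.841, stated as 84%. This point does not touch it.

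**2. Order of events.** SC, then BC (single-blind placebo run-in), then randomisation at Visit 4, then TRC1, TRC2 and PTC. The SC and BC averages are therefore both pre-randomisation values. The PTC model treats one as a covariate and the other as an outcome.

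**3. Precision of the PTC arm difference.** With 1:1 stratified allocation and complete data, the variance of the arm difference at PTC is about 2σ²/n, where n is the number per arm and σ² the residual variance at PTC. The comparison of models is thus the ratio of σ² in the planned model to σ² with SC and BC both as covariates.

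- *From the documents:* SC and BC averages both at least 5; stratum cut at 8; 1:1 allocation; the model terms above.
- *Assumed, because the documents are silent:* pain mean 5.5-6.5, SD 1.7-2, unstructured covariance, one SC slope shared by all cycles, and the between-cycle correlation.

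Large-sample simulation gives:

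| Correlation between cycles | Variance ratio, planned / modified |
|---|---|
| Constant 0.3 | about 1.02 |
| Constant 0.5 | 1.05-1.06 |
| Constant 0.6 | about 1.08 |
| Constant 0.7 | 1.10-1.11 |
| AR(1) 0.5 | 1.00 |
| AR(1) 0.7 | 1.01-1.02 |
| AR(1) 0.8 | 1.04-1.06 |
| AR(1) 0.85 | 1.07-1.09 |

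At the top of this range the SE is √1.11 = 1.054 times as large. The information forgone is 70 × (1 − 1/1.11) = 6.9 women per arm; at a ratio of 1.02 it is 70 × (1 − 1/1.02) = 1.4.

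Wider inputs (SD 1.2-1.5 at SC and BC, 2.0-2.4 later; severe share 12-40%; constant or AR(1) correlation 0.3-0.85; with and without 15% dropout) give a fall in variance from 0 to about 21% when the model is changed. The extreme run, a fall of 21.3%, corresponds to a ratio of 1/(1 − 0.213) = 1.27.

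The change never costs much: at worst about 0.2% of variance in the tabulated scenarios and 0.9% in the wider runs, both under AR(1).

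Most of the difference comes from BC not being a covariate. Having BC as a response rather than leaving it out altogether costs only about 2-3% of variance under constant correlation and under 1% under AR(1).

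**4. Arm-level LS means.** If the strata are weighted equally, the LS mean departs from the observed-margin mean by

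(0.5 − severe share) × stratum coefficient at PTC.

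- Constant correlation 0.6, severe share 26%: observed PTC minus SC is −0.17 and the equal-weight LS mean is +0.06, a shift of 0.23. This implies a stratum coefficient of 0.23/(0.5 − 0.26) = 0.96.
- A wider-input run, AR(1) 0.6, severe share 21%, coefficient 0.52: (0.5 − 0.21) × 0.52 = 0.15.

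Across the central scenarios the shift is about 0.05-0.4 points; the wider inputs give 0.00-0.74.

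What removes it:

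- *Dropping BC from the responses only:* most of the shift remains under constant correlation (0.23-0.36 becomes 0.19-0.28), and it grows slightly under AR(1) (0.14-0.24 becomes 0.16-0.27).
- *BC as a covariate, equal weights:* the shift is close to zero under constant correlation but reverses to −0.12 to −0.21 under AR(1).
- *Observed stratum margins:* the shift is zero to within 0.01 in the planned and the modified model alike.

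**The case against.** The case for leaving the model alone is fair. The analysis is exploratory and unpowered. The objective compares PTC with SC and, unlike the TRC1 objective beside it, does not say versus placebo. The bullet promises LS means, not an arm difference. A profile of change from SC across every later cycle, run-in included, is a coherent display. Even an 11% variance excess is about 5% of an SE, and it rests on correlations nobody has stated.

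Most of this stands and sets the weight of the point. It does not remove it. The model does contain a treatment-by-cycle term. The same section says that continuous exploratory endpoints follow an approach similar to the primary one, which reports the arm difference. The run-in value can still be displayed as an observed mean.

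Two stronger readings are tempting and are not supported:

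- *That the PTC arm difference is biased because a pre-randomisation cycle is treated as an outcome.* Allocation is 1:1 and stratified on BC severity, and stratum-by-cycle is in the model, so the contrast is unbiased. Chance BC imbalance that passes into it is ordinary sampling error, already counted in the SE.
- *That having BC in the response vector shifts the arm-level PTC means by a few tenths of a point.* The shift requires equal stratum weights, which the sSAP does not specify, and it mostly persists when BC merely leaves the responses. An equal-weight LS mean is also a legitimate, if different, summary.

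**Conclusion.** The point holds as a minor improvement. The PTC model models a pre-randomisation cycle as a treatment outcome and leaves its average out of the adjustment. The PTC arm difference stays unbiased, with a variance about 0-11% above what the same data would give with BC as a covariate. The figure depends on assumed correlations: about 2-11% if constant at 0.3-0.7, about 0-9% if AR(1) at 0.5-0.85, and more under wider inputs. No single percentage can be read from the documents.

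The LS-mean weighting is a separate and conditional matter, settled by stating observed margins. Primary and secondary analyses, and the 84% power, are unaffected.

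**What to change.** In the PTC bullet of sSAP 3.6.1:

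1. Remove BC from the response vector, leaving TRC1, TRC2 and PTC as change from SC.
2. Add the BC average as a covariate beside the SC average, matched to the endpoint (overall, cyclic or non-cyclic).
3. If the run-in value is wanted in the display, show it as an observed mean.
4. Separately, state that LS means are computed with observed stratum margins.

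The cost is about two sentences and one degree of freedom. No new data are needed. Eligible participants must already have an overall BC average of at least 5 from at least 75% of diary entries, so the overall analysis should lose nobody to a missing covariate. The model no longer prints an adjusted BC mean.
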